5.1 Description

The PRP product will appear as a liquid.

5.2 Treatment Regimen

The PRP product will be created intra-operatively by personnel from the Division of Transfusion Medicine from a **180** mL sample of the patient's whole blood. An FDA-cleared platelet concentration device (Angel® Concentrated Platelet Rich Plasma [cPRP] System, Cytomedix, Inc., Gaithersburg, MD USA) in routine clinical use at Mayo Clinic in Rochester, MN will be used to create the sample of PRP that will be given one time in topical fashion onto the NVB during nerve-sparing RP. The application of PRP will take approximately 1 minute to perform and the treatment duration for the PRP product is estimated at 4 hours.

5.3 Method for Assigning Subjects to Treatment Groups

Not applicable.

5.4 Preparation and Administration of Study Drug

The PRP sample will be prepared in the operating room from a sample of whole blood while the patient is undergoing RP. The PRP sample will be prepared by trained personnel from the Mayo Clinic Division of Transfusion Medicine. The Division of Transfusion Medicine has developed a detailed SOP that all staff using the Angel® system must follow in order to operate the device (http://mayoweb.mayo.edu/txmed-docs/documents/002696.pdf). At the present time, the Angel® device is used in routine clinical use in the department of orthopedics and physical medicine and rehabilitation at Mayo Clinic in Rochester, MN. In many instances, the Angel® system yields platelet concentrations of approximately 1,000,000 platelets/ mL of plasma. During our planned study we will follow SOP 002696 prior to administration and confirm that the concentration of platelets over baseline be at least 2. This dose of platelets has been

demonstrated to have clinical efficacy and safety for topical applications used in orthopedic and physical medicine and rehabilitation applications.

In addition, the Division of Transfusion Medicine is accredited by the American Association of Blood Banks to perform perioperative activities at Mayo Clinic. Perioperative activities by definition include the intraoperative preparation of PRP. To achieve accreditation, an institution "shall have a structure that clearly defines and documents the parties responsible for the following activities: intraoperative acute normovolemic hemodilution; collection, storage, and administration of autologous blood products obtained during intraoperative and postoperative autologous blood recovery; and perioperative autologous product production. Products covered under these activities include but are not limited to autologous plasma for reinfusion, injection, or topical application, thrombin for topical application, and bone marrow aspirate concentrate for topical application."

The Angel® Concentrated Platelet Rich Plasma (cPRP) System is cleared for use in the U.S. by the FDA as an automated blood cell separator. The device operator's manual states it's indications for use specifically include the following: "To be used in the clinical laboratory or intra-operatively at the point of care for the safe and rapid preparation of platelet poor plasma and platelet concentrate (platelet rich plasma) from a small sample of whole blood or a small mixture of blood and bone marrow. The platelet rich plasma can be mixed with autograft and/or allograft bone prior to applications to an orthopedic site." The Angel device is contraindicated in cases where there is active systemic infection or systemic heparinization. In preparation of this research application we have reviewed the United States government electronic CFR (accessed March 3, 2016 and current as of March 1, 2016) part 1271 entitled "Human Cells, Tissues, and Cellular and Tissue Based Products." We believe that the PRP created in the study would be solely regulated under Section 361 of the Public Health Service Act on the basis of meeting all criteria included in part 1271.10:

- The PRP product created by the Angel® device is minimally manipulated.
- The PRP product created by the Angel® device is intended only for homologous use, following the labeling, advertising, or other indications of the manufacturer's objective intent.
- The PRP product created does not involve the combination of cells or tissues with another article except for water, crystalloid, or a sterilizing preserving or storage agent provided that addition of water, crystalloid, or the sterilizing, preserving, or storage agent does not raise new clinical safety concerns with respect to the product.
- The PRP product created does not have a systemic effect and is not dependent upon the metabolic activity of living cells for its primary function.

Furthermore, according to part 1271.15 from the CFR, we note that our proposed use of PRP would fulfill item (b) that states, "You are not required to comply with the requirements of this part if you are an establishment that removes human cell tissue/products (PRP is an example) from an individual and implants such human cell tissues/products into the same individual during the same surgical procedure.

Since we meet all of the criteria established in part 1271.10 and also meet exception criteria listed in part 1271.15, we believe that the PRP created in this study would be solely regulated

under section 361 of the Public Health Safety Act and that regulation of the created product as a drug under section 351 of the Public Health Service Act would not apply. Accordingly, the need to pursue an IND application for the proposed use was not felt to be applicable. However, upon request for an exemption from IND regulations, FDA subsequently decided to regulate this study under an Investigational Device Exemption, (IDE) for the investigational use of an approved blood separation device.

5.4.1 Specifics of PRP Sample Preparation

To prepare the sample, **180** mL of whole blood will be obtained from the patient by venipuncture during the RP by Anesthesia personnel. The whole blood will be placed in the platelet concentration device and centrifuged following manufacturer's instructions. After final processing, the final PRP sample will consist of 10 mL of product that will be used for intraoperative application. The PRP created intra-operatively would be placed into a syringe labeled "PRP." Samples of whole blood and PRP will also be sent to the laboratory for analysis for quality control purposes, in accordance with Division of Laboratory Medicine SOP. ¹⁰

During the RP procedure, PRP will be applied to the NVB after completion of the vesicourethral anastomosis and after conventional techniques have been performed to achieve adequate hemostasis. Conventional techniques for hemostasis include the placement of surgical clips or suture as required to bleeding sites on the neurovascular bundle. No additional hemostatic products will be applied to the neurovascular bundles during the study. PRP will be applied evenly to the entire length of the NVB by mechanical transfer of product. For robotic procedures, a laparoscopic spoon instrument will be used to deliver the PRP directly to the NVB. For open procedures, delivery of PRP will occur via PRP-labelled syringe. After application of PRP, the surgical team will then complete RP in standard fashion.

5.5 Subject Compliance Monitoring

Not applicable.

5.6 Prior and Concomitant Therapy

The following concomitant medicines are not permitted during the study:

- Any type of androgen deprivation therapy
- Aspirin and heparin for 2 weeks before or 2 weeks after the date of PRP application
- Use of an antidepressant, beta blocker or ED medication at the time of study screening

5.7 Packaging

The PRP will be made intra-operatively and will be placed into a syringe labelled PRP. The PRP will be created from the patient for autologous use and none of the created PRP will be removed from the operating room.

5.8 Masking/Blinding of Study

Not applicable

5.9 Receiving, Storage, Dispensing and Return

5.9.1 Receipt of Drug Supplies

Not applicable

5.9.2 Storage

Not applicable

5.9.3 Dispensing of Study Drug

Not applicable

5.9.4 Return or Destruction of Study Drug

Not applicable

6 Study Procedures

6.1 Visit 1; Screening and Baseline

Potential study subjects will be identified by study staff, will be provided ample time to review the informed consent document, discuss the study procedures and contents of the ICF, have all questions answered, have their medical history reviewed, vitals taken, and a physical examination performed. The baseline quality of life assessments with Sexual Health Inventory for Men and the Expanded Prostate Cancer Index Composite will be completed by the subject at this visit, if not done earlier. Baseline CBC with differential and platelet count and serum PSA samples will be obtained. If a PSA and CBC with differential and platelet count have not been performed during clinic visits at Mayo Clinic within the year prior to the screening visit and the subject has scheduled clinical labs before the screening visit, an order will be placed for the baseline PSA and CBC with differential and platelet count to ensure there is proper record of test result in the Mayo Clinic medical record. If a PSA and CBC with differential and platelet count have been performed outside of Mayo Clinic within the year prior to the screening visit and the subject does not have scheduled clinical labs before the screening visit, outside results may be used to satisfy this study visit with copies retained in study files. The study coordinator will confirm the contact information of the outside laboratory facility at the time of the screening visit and will request outside laboratory results if not already available in the Mayo Clinic medical record. However, all study eligibility requirements; including a review of current medical conditions and medications as well as written informed consent must be documented by study staff and reviewed for acceptability by an Investigator prior to enrolling the subject into the Documentation of any subjects who were consented but subsequently failed the screening requirements, including the reason for screen failure, will be retained in study files. A screening/enrollment log will be maintained.

6.2 Visit 2; Surgery

At the time of radical prostatectomy, topical PRP will be prepared and applied topically to the NVB. An assessment of adverse events will be conducted via medical record review by the study coordinator.

6.3 Visit 3: Post-operative Day 2 (POD 2)

Subjects will undergo a review of their medical status and a physical examination. There will be a blood draw to assess CBC with differential and platelet count. An assessment of adverse events will be conducted by the study coordinator via medical record review. For visit 3 only, vital sign readings taken as part of standard of care will be abstracted via medical record review by the study coordinator.

6.4 Visit 4: Week 1

At approximately 1 week after surgery, the urinary catheter placed at the time of RP will be removed. This visit is timed at one week post RP to allow for the typical healing period prior to removal of catheter. If clinically indicated, the healing period may require more than 7 days, therefore this study visit may occur up to 21 days following the RP. This visit may be completed remotely rather than on-site, if the subject decided to have urinary catheter removal done locally. Contact with the subject may be by telephone or email, depending upon subject preference. The subject will undergo a postoperative check by study staff where quality of life status will be assessed with questionnaires. The Questionnaires may be mailed to the subjects (if visit is done remotely) with a self-addressed, postage paid, return envelope for completion and return to the study site by email, fax or regular mail and will be retained with subject study files. A physical examination by a Study Investigator will be performed and vitals will be taken if visit is completed on-site. An assessment for adverse events and concomitant medications review will be conducted by the study coordinator. Outside records for physical exam and vitals will be requested if visit is done remotely. The RP date will be considered Day 0 for determining future study visit windows. Per protocol, serum PSA has not been collected at this point and will continue to not be collected for remote visit

6.5 Visit 5: Week 12

At approximately 12 weeks after surgery, with an allowable visit window of +/- 14 days, subjects will undergo a postoperative check by study staff where quality of life status will be assessed with questionnaires. The Questionnaires may be mailed to the subjects with a self-addressed, postage paid, return envelope or emailed to the subjects for completion and return to the study site by email, fax or regular mail and will be retained with subject study files. This study visit may be completed remotely rather than on-site, if more convenient for the subject. Contact with subject may be by telephone or email, depending upon subject preference. Subjects will undergo a physical examination by a Study Investigator, have vitals taken, and have a serum PSA sample drawn. Adverse events will be assessed and concomitant medications will be reviewed by study coordinator. Outside records for physical exam and vitals will be requested by study staff if visit is done remotely. For subjects returning to the institution, the PSA sample will be drawn in the Mayo Clinic clinical laboratory. For subjects completing a remote visit, serum may be collected locally using a "mail-in" PSA kit mailed to the subject by study staff. This kit will be mailed back to Mayo Clinic for testing. The allowable PSA testing window is +/- 21d.

6.6 Visit 6: Month 6

At approximately 6 months after surgery, with an allowable visit window of +/- 14 days, subjects will undergo a study visit which may be completed remotely rather than on-site, if more convenient for the subject. Contact with subject may be by telephone or email, depending upon subject preference. The Questionnaires may be mailed to the subjects with a self-addressed,

postage paid, return envelope or emailed to the subjects for completion and return to the study site by email, fax or regular mail and will be retained with subject study files. For remote visits, the subject will be contacted to assess changes in concomitant medications and to assess if any adverse events have occurred since the previous study visit. Information obtained during telephone calls or other contact will be documented in the subject's study file. A serum PSA sample will be obtained. For subjects returning to the institution, the PSA sample will be processed in the Mayo Clinic clinical laboratory. For subjects completing a remote visit, serum may be collected locally using a "mail-in" kit to be mailed to the subject by study staff. This kit will be mailed back to Mayo Clinic for testing. Venipuncture may be obtained by a local physician or clinic. The allowable PSA testing window is +/- 21d.

6.7 Visits 7, 8 and 9: Months 9, 12 and 18

At approximately 9, 12 and 18 months after surgery, with allowable visit windows of +/- 14 days, subjects will undergo a study visit which may be completed remotely rather than on-site, if more convenient for the subject. For remote visits, the SHIM and EPIC Questionnaires may be sent to the subjects for completion and returned to the study site by mail, fax or email. A telephone call to the subject will be made to assess changes in concomitant medications and if any adverse events have occurred since the previous study visit. A serum PSA sample will be obtained. For subjects returning to the institution, the PSA sample will be analyzed in the Mayo Clinic clinical laboratory. For subjects completing a remote visit, the PSA sample may be obtained with venipuncture obtain locally and returned using a "mail-in" kit with analysis to be performed by the Mayo Clinic laboratory. The allowable PSA testing window is +/- 21d.

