1.5 Dose Rationale and Risk/Benefits

The PRP sample will be prepared in the operating room from a sample of whole blood while the patient is undergoing RP. The PRP sample will be prepared by trained personnel from the Mayo Clinic Division of Transfusion Medicine using a commercially available, FDA-cleared, platelet concentration device in accordance with the manufacturer's instructions ((510K# BK110046; Angel® Concentrated Platelet Rich Plasma [cPRP] System, Cytomedix, Inc., Gaithersburg, MD USA). The Division of Transfusion Medicine has developed a detailed SOP that all staff using the Angel® system must follow in order to operate the Angel® device (http://mayoweb.mayo.edu/txmed-docs/documents/002696.pdf).

At the present time, the Angel® device is used in routine clinical use in the department of orthopedics and physical medicine and rehabilitation at Mayo Clinic. The Angel® system yields platelet concentrations of approximately 1,000,000 platelets/ mL of plasma. This dose of PRP has been demonstrated to have clinical efficacy and safety for topical applications used in orthopedic and physical medicine and rehabilitation applications.

Clinical experience with the Angel® device has demonstrated that a sample of 180 mL of whole blood will yield approximately 10 mL of PRP. This dose would be divided equally and will permit even topical application to the NVB intra-operatively at RP. The study proposes a one-time dosage period and clinical studies to date report that the duration of action for PRP is approximately 4 hours.

Risks from study participation may be related to obtaining the whole blood to produce the PRP sample or the effects of the PRP sample on the healing process after surgery. The collection of

blood would be obtained under general anesthesia required for RP using sites needed for the general anesthetic. Obtaining the whole blood could results in pain, bruising, and infection at the needle site. Obtaining a collection of blood could also have an adverse effect the patient's circulating blood volume and could result in lightheadedness or hypotension after surgery. In some instances this could require that a blood transfusion be given. Since the risk of blood transfusion for RP ranges from <1 to 5%, the independent risk of the blood collection alone requiring a postoperative blood transfusion is very low.

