8.2 Recording of Adverse Events

At each contact with the subject, the study team must seek information on AE by specific questioning and, as appropriate, by examination. Information on all adverse events should be recorded immediately in the source document, and also in the appropriate AE section of an electronic adverse event worksheet. All clearly related signs, symptoms, and abnormal diagnostic, laboratory or procedure results should recorded in the document.

All adverse events occurring during the study period must be recorded. The clinical course of each event should be followed until resolution, stabilization, or until it has been ultimately determined that the study treatment or participation is not the probable cause. Serious adverse

events that are still ongoing at the end of the study period must be followed up, to determine the final outcome. Any serious AE that occurs after the study period and is considered to be at least possibly related to the study treatment or study participation should be recorded and reported immediately.

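### At postoperative day 2, section 6.3 names chart review as the adverse-event method although 8.2 requires specific questioning at each contact, so patient-reported acute events may be missed

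*Combined protocol and SAP*

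**What the plan says.** Sections 6.2 and 6.3 name the method of adverse-event assessment for the first two visits at or after surgery. For the surgery visit: "An assessment of adverse events will be conducted via medical record review by the study coordinator". For POD 2: "An assessment of adverse events will be conducted by the study coordinator via medical record review". Section 6.3 also plans direct contact with the patient that day: "Subjects will undergo a review of their medical status and a physical examination". A blood count is drawn at the same visit, and vital signs are abstracted from the record.

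The general rule is in 8.2: "At each contact with the subject, the study team must seek information on AE by specific questioning and, as appropriate, by examination". The same section adds: "All adverse events occurring during the study period must be recorded".

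The next assessment is the Week 1 visit (6.4), planned at about one week but allowed up to 21 days after surgery, on site or remotely. Its text reads: "An assessment for adverse events and concomitant medications review will be conducted by the study coordinator". It is not limited to chart review, and it states no look-back period. The schedule of events (6.8) marks an adverse-event evaluation at POD 2 without naming a method.

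On the risks of the blood collection, 1.5 says: "Obtaining the whole blood could results in pain, bruising, and infection at the needle site". It also lists lightheadedness or hypotension after surgery, and a possible transfusion.

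**The concern.** Safety and tolerability form the primary objective (sections 2 and 3.2), and the Study Summary says that the adverse events counted will include local reactions. The 180 mL blood draw and the single PRP application both fall on the day of surgery. POD 2 is the first scheduled visit after the operation at which the patient can be asked how he has felt since.

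A coordinator who follows the visit-specific text can complete the POD 2 assessment from the chart alone and satisfy 6.3 without doing what 8.2 requires. A brief symptom that nobody asks about may never be charted. With 20 subjects and a descriptive analysis, one or two unrecorded events would visibly change the reported tolerability.

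**Working it through.** The documents state no figure for completeness of adverse-event capture, and the sample size of 20 (7.1) is not derived from an event rate. There is no plan figure to reproduce, so the check is mainly a comparison of texts.

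1. **Is POD 2 a contact under 8.2?** Yes. Section 6.3 schedules a status review, a physical examination and a blood draw. Section 8.2 makes no exception for this visit.

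2. **Do 6.3 and 8.2 name the same method?** No. Section 8.2 requires specific questioning by the study team. Section 6.3 names record review by the coordinator. The schedule in 6.8 gives no method and does not settle the matter.

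3. **Does the same apply to the surgery visit?** Not clearly. Section 1.5 says that "blood would be obtained under general anesthesia required for RP". A man under general anesthesia cannot be questioned during the procedure, so chart review is a reasonable method for that visit.

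4. **Which listed risks depend on asking?** Section 1.5 gives six for the blood collection: needle-site pain, bruising, infection, lightheadedness, hypotension and transfusion. Pain and lightheadedness, two of the six, are purely reported symptoms. The others can be seen on examination or found in the record.

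5. **Does a later visit clearly recover days 0 to 2?** It may. The Week 1 assessment has no stated look-back. One is written out only for remote contacts from Month 6 onward (6.6, 6.7), and it runs to the previous visit. If that convention were applied at Week 1, the previous visit would be POD 2, and the interval would begin after the acute period.

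The following illustration shows why capture matters at n = 20. All inputs except n are assumed. Let p be the true proportion of men with an acute event and s the share of those events that is recorded, with no recovery at later visits. The chance of recording at least one event is 1 − (1 − p·s)^20.

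| p | s = 100% | s = 90% | s = 75% | s = 50% |
|---|---|---|---|---|
| 5% | 64.2% | 60.2% | 53.4% | 39.7% |
| 10% | 87.8% | 84.8% | 79.0% | 64.2% |
| 20% | 98.8% | 98.1% | 96.1% | 87.8% |

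For example, p = 10% and s = 50% give 1 − 0.95^20 = 64.2%.

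If 0 of 20 events were recorded, the exact one-sided 95% upper bound on the recorded rate would be 1 − 0.05^(1/20) = 13.9%. Dividing by s gives the corresponding bound on the true rate: 15.5% at s = 90%, 18.5% at 75% and 27.8% at 50%. These values show sensitivity to the assumptions. They do not estimate what will happen in this trial.

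**The case against.** The strongest reply is that the two sections can be read together. Section 6.3 does not say that chart review is the only method. Clinical staff see the patient on POD 2, their findings enter the record, and the coordinator abstracts them, while 8.2 continues to bind the study team. Objective harms are well covered by the blood count, the vital signs, the rule in 8.1 that a POD 2 hemoglobin below 8 g/dL is an adverse event, and the planned evaluation of complications and transfusion. The product-specific risks in 1.5, adverse healing and cancer recurrence, are followed to month 18 and do not depend on POD 2 questioning. In a single arm, needle-site pain or lightheadedness after major surgery is also hard to attribute to the study procedure.

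Much of this stands. The status review may bring some symptoms into the chart, and the gap concerns a minority of the listed risks. However, a status review is not specific questioning about adverse events, which is what 8.2 asks for, and nothing in 6.3 says that the coordinator or anyone else must do it. Difficulty of attribution is no reason to leave an event unrecorded when 8.2 requires all of them.

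A reader might also infer that the first questioning of any kind comes at Week 1, perhaps on day 21. The documents do not establish this. Section 8.2 still applies at POD 2, and day 21 is the outer limit of a visit planned at about one week.

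**Conclusion.** The point holds for POD 2 as an inconsistency that creates a risk of missing patient-reported acute events in the primary safety and tolerability evaluation. It is minor, it is cheap to correct, and it has no bearing on sample size or error rates.

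Two stronger readings are not supported. The first is that acute events are in fact under-counted. No passage gives or implies a capture share, some symptoms may reach the chart or be recovered at Week 1, and so neither the existence nor the size of an under-count can be computed. The second is that 6.2 is equally at fault. Under general anesthesia it is not.

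Nor can a direction of bias be claimed against the registry comparator (3.1, 8.6), because the documents do not describe how adverse events are ascertained there.

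The conclusion rests on reading the POD 2 visit as a contact within the meaning of 8.2, which the content of 6.3 supports.

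**What to change.** Reconcile 6.3 with 8.2. State in 6.3 that at the existing POD 2 contact study staff ask specifically about adverse events since surgery, including needle-site symptoms, lightheadedness and local reactions, and that medical record review is kept as a supplement. State in 6.4 that the Week 1 assessment looks back to the day of surgery. Section 6.2 can stay as it is.

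The cost is a few minutes per subject, with no added visit. The recorded count of minor events will probably be somewhat higher. Ascertainment may also become more active than in the registry, and this should be noted wherever the two groups are compared on safety.
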